8.1 Inclusion criteria

All English speaking pregnant women 27 – 30 weeks pregnant who are considering breastfeeding will be eligible for inclusion in this study. We have chosen to recruit and consent women who are considering breastfeeding to peer-supporters in the antenatal period so that we can investigate if antenatal contact facilitates the development of supportive relationships and early contact with the peer-supporter after birth. The first few days after birth is the period when there is a steep reduction in breastfeeding rates, and early postnatal peer-support has not been previously evaluated. Women with multiple pregnancies (twins, triplets etc) will be eligible for inclusion in the study as long as they meet the other inclusion criteria. This will allow us to explore the feasibility of providing MI based breastfeeding peer-support to this group of women.

8.2 Exclusion criteria

- unable to provide written informed consent
- unable to converse in conversational English
- do not plan to breastfeed
- clinical reason that precludes breastfeeding (e.g. major congenital anomaly)
- Planned admission to neonatal unit following birth
- Participant in qualitative development work

9 Outcome measures

9.1 Primary outcome measure

Breastfeeding at 8 weeks after birth

9.2 Secondary outcome measures

Data will also be collected using a range of maternal health and wellbeing measures, shown in appendix 2.

10 Recruitment and registration

10.1 Number of participants

Qualitative development work: A total of 22-32 parents, 12-16 peer supporters and 12 health professionals and managers will be recruited.

Feasibility testing: A total of 110 participants will be recruited at a rate of around 37 per centre.

10.2 Recruitment process

Qualitative development work

For the qualitative development work we will recruit parents from existing parenting groups in each of the three research sites, facilitated by local collaborators ([name], [name], [name]). Peer supporters will be recruited by local managers from existing databases of peer supporters, co-ordinated by [name] and [name]. Health professionals and managers will be recruited using existing networks of study co-applicants and collaborators.

Recruitment of peer supporters for feasibility study:

We will recruit 6-9 peer supporters (2-3 in each of the study sites) who have completed accredited BFPS training. We will use a formal advertisement and interview process in order to recruit from the existing database of peer-supporters in the three study areas. We will access these peer-supporters through midwifery and health visiting staff who support volunteers and maintain local databases of peer supporters (approximately 40 peer supporters per area), local breastfeeding groups, supervision and update sessions (where these are available) and from local Facebook sites where they are freely accessible in the public domain. Additional ways of disseminating the advertisement may be included following the focus groups with peer supporters in objective 2.

Recruitment of local study midwives for feasibility study:

We will recruit one practicing midwife in each site to provide support to peer supporters delivering the feasibility study intervention. [name], [name] and [name] will request expressions of interest for the role, in collaboration with heads of midwifery.

Recruitment of feasibility study participants

Potential participants (n=800) will be identified in conjunction with staff from maternity teams providing antenatal care in the study areas. Midwives will introduce the study to pregnant women at around 28 weeks gestation and obtain agreement to forward the potential participants' contact details to the research team. Women who participated in the qualitative development work will be excluded from this element of the study.

Recruitment pathways will be informed by the qualitative work with Health care professionals in Objective 2 and tailored to accommodate local variations in clinical practice pathways and services at each study site. The researcher will contact identified potential participants by telephone to assess eligibility (i.e. pregnant women considering breastfeeding their baby), and if eligible, and agreeable to the woman, the researcher will arrange a recruitment visit where they will be provided with an information pack explaining the study. Adequate time will be given for reading the material and opportunities provided to ask any questions. Women will be encouraged to discuss the study with friends and family, if needed, before deciding about participation. The researcher will obtain informed written consent (including consent for long-term follow up using data-linkage), complete a baseline assessment (at 30-34 weeks gestation), and provide the participant with the contact details of the study peer-supporter working in the area. The study manager will inform the peer-supporter, of each new recruit, who will then take responsibility to contact the participant to provide MI based BFPS as specified in Objective 3. The research team have experience from the Building Blocks study (44) of using this method for recruitment and we will test the feasibility and applicability of this approach (modified as indicated by the findings from the qualitative work in objective 2).

10.3 Informed consent

The researcher will obtain written informed consent (including consent for long-term follow up using data-linkage). Standardised consent forms will

be approved by the NHS REC, and the study manager will use the most up to date version held in the Trial Master File.

10.4 Randomisation/registration and unblinding

The study will not involve randomising participants.

10.5 Screening logs

A screening log, which will not contain any personal information, of all prima facie eligible women who refuse participation in the study will be kept at each site, and will be updated by midwives. The screening log should be sent to the study manager every month (see section 19 for further detail on data monitoring/quality assurance).

Alongside this, records of ineligible and eligible but not consented women will be kept by the study manager so that any biases from differential recruitment will be detected.

11 Withdrawal & loss to follow-up

11.1 Mandatory withdrawals

Following recruitment in the antenatal period, women who with the following criteria will be withdrawn from the study:

- Preterm birth (<37 weeks gestation)
- BF not initiated
- Clinical reason that precludes BF continuation (e.g. major congenital anomaly)

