3.3 Study summary

Design:

- (i) Rapid evidence review and qualitative research to inform development of a novel breastfeeding peer-support (BFPS) intervention that uses a motivational interviewing (MI) approach for breastfeeding (BF) maintenance
- (ii) A non-randomised multi-site study to test the feasibility of delivering MI based BFPS to mothers living in areas with high levels of social deprivation. A visual representation of our design can be found on page 11.

Evidence review strategy: Web-based survey of UK service providers and search of 14 databases to characterise the range of BFPS programmes used in current practice, identifying underpinning theoretical models and implementation issues.

Intervention development: Focus groups with potential service users (n=18-24), fathers (n=4-8) and peer supporters (n=12-16), interviews with midwives, health visitors and service managers (n=9) to inform content of MI based BFPS, implementation and research processes. The Behaviour Change Wheel framework will be used to map the identified sources of behaviour and intervention functions for BFPS identified in the qualitative work and evidence review to generate a structured theorydriven framework that incorporates MI in the BFPS intervention. The specification of MI based BFPS and corresponding logic model will be finalised in consultation with stakeholders. One of the four planned stakeholder advisory group meetings will be convened in month 2, to allow discussion of the rapid review findings and consideration of the areas to be discussed during the focus groups. This will be followed by subsequent meetings during months 4 to 7 to validate the mapping of our findings from the rapid review and focus groups on to the Behaviour Change Wheel framework, and advise on the final specification of the MI based BFPS intervention and corresponding logic model.

Feasibility testing:

Setting: Community maternity services in three areas with high levels of social deprivation and low BF initiation rates in England and Wales.

Population: Pregnant women considering breastfeeding.

Exclusion: Inability to consent, unable to converse in conversational English.

Sample size: 6-9 peer-supporters (2-3 per site) will deliver BFPS to 90-99 mothers, over a 6-month period.

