Women who are considering breastfeeding will be provided with the opportunity to receive breastfeeding support from a trained peer supporter. Participants will receive at least one antenatal contact, and contact within 48 hours of birth. It is anticipated that support will be most intense within two weeks of birth. The full content and specification of this will be defined during the development phase (objectives 1-3), and this protocol will be updated. For example, we will consider using a 24hour telephone number for the delivering midwife to leave a message at any time; stickers on the woman's maternity notes with the individual peer supporter's name and phone number, to be rung and message left either by the woman, partner or midwife shortly after the birth.

13 Adverse Events

Adverse Event (AE): Any untoward medical occurrence in a study participant which does not necessarily have a causal relationship with this treatment. An AE can therefore be any unfavourable and unintended sign (including abnormal laboratory finding), symptom, or disease.

Serious Adverse Event (SAE): Any adverse event, affecting either the mother or baby, that:

- Results in death
- Is life-threatening*
- Required hospitalisation or prolongation of existing hospitalisation (for reasons other than the birth of the baby)**

- Results in persistent or significant disability or incapacity
- Consists of a congenital anomaly or birth defect
- Other medically important condition ***

* Note: The term "life-threatening" in the definition of serious refers to an event in which the participant was at risk of death at the time of the event; it does not refer to an event which hypothetically might have caused death if it were more severe.

** Note: Hospitalisation is defined as an inpatient admission, regardless of the length of stay, even if the hospitalisation is a precautionary measure, for continued observation. Pre-planned hospitalisation e.g. for the birth of the baby or pre-existing conditions which have not worsened or elective procedures does not constitute an adverse event.

*** Note: other events that may not result in death are not lifethreatening, or do not require hospitalisation may be considered as a serious adverse event when, based upon appropriate medical judgement, the event may jeopardise the participant and may require medical or surgical intervention to prevent one of the outcomes listed above.

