15.2 Sample size

This feasibility study is not powered to detect statistical significance.

16 Analysis

Objective 1

Descriptive statistics will be used to show the current range of UK BFPS using data generated from the web-based survey of service providers. A narrative synthesis will be used to critique and summarise the characteristics of UK BFPS and any underpinning theoretical models.

Objective 2

Focus groups and interviews will be audio recorded and transcribed verbatim. Transcripts will be input into NVivo 10, and will be analysed using framework analysis (87) based on concepts within the Behaviour Change Wheel framework (9). This will allow the data to be analysed in a

structured way which is particularly helpful during intervention development and evaluation. The coding framework will include the items on the topic guide, as well as additional codes including barriers and facilitators to implementing and using the intervention. A random sample of 30% of transcripts will be coded by a second researcher, and any inconsistencies will be discussed and resolved.

Objective 3

We will map the theoretical models identified in the evidence review (objective 1) and the results from the qualitative work (objective 2) against the Behaviour Change Wheel framework (9) to specify the relevant sources of behaviour and corresponding intervention functions, and develop a logic model for the intervention.

Objective 4 – Quantitative data

We will use the quantitative data generated from objective 4 of the study to describe intervention uptake by mothers, completion of scheduled contacts with peer-supporters according to age-group and parity, recruitment and retention of peer-supporters, completeness of peer supporter diaries, follow-up of participants at 8 weeks, breastfeeding rates at initiation and at 8 weeks and other outcome measures described in Table 1, using percentages and 95% confidence intervals for categorical data and mean, standard deviation (s.d.) and 95% confidence intervals for continuous data. Thus summary data for the whole group and by site will provide information relevant to inform a full trial. The inter-class correlation will be estimated from the site data regarding variation in breast feeding outcome using ANOVA. We will describe completeness of data collected according to the different data collection methods described in appendix 1.

Objective 4 – Qualitative data

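### Section 11.1 takes women out of the whole study for events after consent, one of which (not starting to breastfeed) is itself a planned outcome, so their 8-week follow-up is lost

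*Protocol*

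**What the plan says.** Women are recruited antenatally (protocol 8.1 and 10.2), and part of the intervention comes before birth: "Participants will receive at least one antenatal contact, and contact within 48 hours of birth" (12.1).

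Section 11.1 then says: "Following recruitment in the antenatal period, women who with the following criteria will be withdrawn from the study". The listed criteria include "Preterm birth (<37 weeks gestation" and "BF not initiated"; the third is a clinical reason that rules out continued breastfeeding.

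Section 11.2 separates withdrawal from the intervention, from follow-up (including qualitative interviews), and from the entire study with no use of data. It does so for elective withdrawal. Section 11.1 uses none of these narrower categories and does not say whether follow-up continues or data are kept.

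Section 9.1 names breastfeeding at 8 weeks as the primary outcome. Section 16 (Objective 4, quantitative data) plans to describe uptake, follow-up, and "breastfeeding rates at initiation and at 8 weeks and other outcome measures described in Table 1", with 95% confidence intervals. No denominator is given for any of these.

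**The concern.** One ground for removal, non-initiation, is also a result that the study intends to report. Section 11.2 shows that the protocol has a term for leaving support while staying in follow-up. The natural reading of 11.1 is therefore that these women leave everything, including the 8-10 week telephone interview (14.1, 14.4) and its outcomes on health, satisfaction and service use (Appendix 2). They would also leave the pool for process-evaluation interviews, although section 14.2 wants that sample to vary by breastfeeding success and by engagement.

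Two things are at stake. First, information is lost on women whom the study recruited deliberately: section 8.1 explains that antenatal recruitment is meant to show whether antenatal contact helps early contact after birth. Second, an 8-week rate computed only in women who remain describes term initiators. It could be read as the rate for all women recruited in pregnancy, and so overstate it. Section 10.5 keeps records to detect bias from differential recruitment, but nothing comparable covers exclusion after recruitment.

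**Working it through.** The protocol states no initiation, follow-up or 8-week figure for this cohort, so there is no planned result to reproduce. The one arithmetic check on recruitment is 3 sites × 37 = 111, which agrees with the stated 110.

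**Inputs**
- N = 110 recruited (section 10.1).
- i = proportion initiating. Section 4.1 gives 81% for the UK. The values 70% and 90% are assumptions. Section 7 selects sites with breastfeeding rates below 70%, but that is a site average and not the rate in women already considering breastfeeding.
- m = proportion of initiators still breastfeeding at 8 weeks. Section 4.1 says about two-thirds of initiators stop before 6 weeks, so m ≈ 1/3, used as a proxy for 8 weeks.
- Non-initiators count as not breastfeeding at 8 weeks. No other withdrawals in this calculation.

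**Formulae**
- All recruited: initiation = i; 8-week rate = i × m.
- Women remaining: initiation = 100%, because every non-initiator has been removed; 8-week rate = m.
- Ratio of the two 8-week rates = m / (i × m) = 1/i.

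**Results** (rounded to whole women; 95% Wilson intervals)

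| Initiation | Initiators | Breastfeeding at 8 weeks | Rate, all 110 | Rate, women remaining | Ratio |
|---|---|---|---|---|---|
| 70% (assumed) | 77 | 26 | 26/110 = 23.6% (16.7-32.4) | 26/77 = 33.8% (24.2-44.9) | 1.43 |
| 81% (section 4.1) | 89 | 30 | 30/110 = 27.3% (19.8-36.3) | 30/89 = 33.7% (24.7-44.0) | 1.24 |
| 90% (assumed) | 99 | 33 | 33/110 = 30.0% (22.2-39.1) | 33/99 = 33.3% (24.8-43.1) | 1.11 |

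The ratio does not depend on m, apart from rounding, so the choice of continuation proxy affects the level of the rates and not their relative distortion.

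**Uptake.** Antenatal contact precedes withdrawal, so the direction is open. Assume 81% initiation and 70% uptake in women who remain. Uptake in all recruited is 0.81 × 0.70 + 0.19 × u, where u is uptake in withdrawn women. With u = 40% this gives 64%; with u = 70%, 70%; with u = 85%, about 73%. All these uptake values are assumptions.

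**The case against.** The strongest reply is that section 11.1 does not dictate the analysis. No denominator is fixed, and analysis populations are commonly left to the statistical analysis plan. Non-initiation is the recorded reason for withdrawal, so initiation out of all 110 can be rebuilt. Only the elective category in 11.2 mentions not using data. A rate among initiators is also a legitimate measure for a study of breastfeeding maintenance, if labelled as such. The 95% intervals are about 16 to 21 percentage points wide in a study that is expressly not powered, so the shift is modest. All of this stands, and it is why the distortion is conditional. It does not answer the loss of follow-up: a later document can choose denominators but cannot supply interviews that were never held.

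A reader might infer several stronger points that the documents do not support:
- **Inflated uptake and follow-up percentages.** The uptake calculation moves either way. Percent follow-up rises only if withdrawn women leave the denominator and would have been followed less often.
- **Upward bias from removing preterm births.** Preterm mothers may breastfeed, so the direction is unknown. Only the non-initiation criterion gives a definite upward shift.
- **A biased decision to proceed.** Section 6 (item 6) ties progression to whether delivery is feasible and acceptable and sets no 8-week threshold. The full trial's sample size is to draw on routine NHS rates, the web survey and stakeholder discussion.
- **A rule that defeats the inclusion of multiple pregnancies.** Section 8.1 says "Women with multiple pregnancies (twins, triplets etc) will be eligible for inclusion in the study", subject to the other criteria. The protocol gives no preterm share for multiples, and recruitment and antenatal contact stay observable.
- **An error in the numbers.** "A total of 110 participants will be recruited at a rate of around 37 per centre" (10.1) and "will deliver BFPS to 90-99 mothers, over a 6-month period" (3.3) differ by 11 to 20 women, or 10.0% to 18.2%. That is compatible with planned attrition, although the protocol does not say what it covers.

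**Conclusion.** The concern holds in limited form and should be fixed. Section 11.1, as written, ends study participation for events after consent, one of which is a planned outcome, and so removes these women from the 8-10 week follow-up and the interview pool. If rates are then taken in the women who remain, the initiation rate carries no information and the 8-week rate is about 1.1 to 1.4 times the rate in all recruited women (1.24 at 81% initiation).

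That size rests on the assumed 70% and 90% limits, on national initiation applying to this cohort at the central value, and on counting non-initiators as not breastfeeding. It applies only if the denominator is the women who remain, which the protocol neither states nor excludes. No effect of determined direction is shown for uptake, percent follow-up or preterm removal, and none on progression to a full trial.

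**What to change.** - **Section 11.1:** replace the instruction to withdraw from the study with wording that keeps these women in study follow-up unless they elect to withdraw. Where a telephone call would be insensitive, use health visitor or routine data, which section 14.1 already proposes to explore. State separately whether peer support continues; that is a matter for the study team and is not prejudged here.
- **Section 16:** report initiation and 8-week breastfeeding with all recruited women as denominator, counting non-initiators as not breastfeeding. Show the maintenance rate in term initiators separately and labelled. Report counts by withdrawal reason.
- **Section 14.2:** keep these women eligible for process-evaluation interviews.

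The cost is protocol wording, ideally before recruitment starts, and roughly 10-30 further follow-up contacts with women who have already consented (11 to 33 non-initiators at 90% to 70% initiation, before any preterm births or clinical reasons). Some contacts will be sensitive, particularly after a major congenital anomaly; section 13.2 already wants the team to know of anomalies before contacting the family. Some reported rates will be less favourable.

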11.2 Elective withdrawals

Participants have the right to withdraw consent to participation in any aspect of the Peer support for breastfeeding maintenance study at any time. The participant's care will not be affected at any time by declining to participate or withdrawing from the study.

If a participant initially consents but subsequently withdraws from the study, clear distinction must be made as to what aspect of the study the participant is withdrawing from. These aspects could be:

1. Withdrawal from qualitative development work

- 2. Withdrawal from study intervention
- 3. Withdrawal from study follow-up, including qualitative interviews
- 4. Withdrawal from entire study and does not want data to be used.

A participant may withdraw or be withdrawn from the intervention for the following reasons:

- > Withdrawal of consent for intervention by the participant
- Any alteration in the participants condition or circumstances which justifies the discontinuation of the intervention in the Investigators opinion

In all instances participants who consent and subsequently withdraw should complete a withdrawal form (see Withdrawal Form in study pack) or the withdrawal form should be completed on the participant's behalf by the researcher/clinician based on information provided by the participant. This withdrawal form should be sent to the Peer support for breastfeeding maintenance Study Manager. Any queries relating to potential withdrawal of a participant should be forwarded to the Study Manager immediately.

